Recently a genetic variant in the *SLCO13* gene (rs2117032-C/T) was found to have a strong association with bilirubin levels in neonates [64]. In order to try to identify potential predisposing factors that might be associated with elevated bilirubin levels in the study population, the UGT1A1 and *SLCO1B3* (rs2117032) genetic variant will be evaluated at the end of the study.

Table 9:
Mean (SD) unbound bilirubin concentrations ($\mu\text{g/dL}$) with no additional drug or in presence of varying concentrations of raltegravir or sulfisoxazole.
*Significantly greater than no drug ($p \leq 0.05$)

Total Bilirubin	No Drug	Raltegravir (μM)					Sulfisoxazole (μM)	
		5	10	100	500	1000	500	1000
10.7 mg/dL	3.46	3.39	3.37	3.95	4.87	6.11	6.60	8.64
	(0.25)	(0.22)	(0.18)	(0.30)*	(0.24)*	(0.26)*	(0.25)*	(0.17)*
18.8 mg/dL	7.60	7.80	8.04	8.39	10.28	11.22	10.77	-----
	(0.27)	(0.32)	(0.18)*	(0.71)*	(0.46)*	(0.72)*	(0.36)*	

Figure 2
Mean (SD) unbound bilirubin concentrations ($\mu\text{g}/\text{dL}$) with no additional drug or in presence of varying concentrations of raltegravir or sulfisoxazole.

[figure not shown]

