A minimum of 20 evaluable infants will be enrolled into Cohort 2 to receive raltegravir for 6 weeks in addition to standard of care ARV for PMTCT prophylaxis. Cohort 2 dosing has been determined based upon modeling and simulation analyses, which included data generated from IMPAACT P1097, P1066 (Cohorts IV and V), P1026s, and P1110 Cohort 1 and incorporated information about UGT1A1 ontogeny to inform the development of neonate metabolic pathways. RAL-naïve infants in Cohort 2 will receive RAL at a dose of 1.5 mg/kg daily as oral granules for suspension starting within 48 hours of birth. RAL-exposed infants in Cohort 2 will receive RAL at a dose of 1.5 mg/kg daily as oral granules for suspension starting within 12 to 60 hours of birth. Additionally, RAL dosing in Cohort 2 may be modified based on ongoing interim analysis of pharmacokinetic data and safety information.

All Cohort 2 infants will have a history, physical examination, and hematology (except for the After Second Dose visit) and chemistry laboratory evaluations performed at all study visits. Additional repeat total and direct bilirubin will be done on day 2-4 of life (after the second dose). Follow-up visits will occur at Day 6-9, Day 15-18, Day 28-32, and 5-6 weeks, 8-10 weeks and 24 weeks of life.

Note: Cohort 1 (RAL-exposed and RAL-naïve groups) and Cohort 2 (RAL-naïve group) were fully enrolled under protocol Version 1.0 and the results of Cohort 1 were used to inform the dosing regimen for Cohort 2, see protocol Section 1.29 for a summary of these results.

Pharmacokinetic sampling for infants in Cohort 2 will include the following:

*Note: PK sampling will ideally be scheduled after RAL has reached steady state (approximately 7-10 days after the dose increase). For example, the Day 15-18 PK sampling collection visit should ideally be scheduled 7-10 days after the infant received his/her RAL dose regimen increased from 1.5 mg/kg once daily to 3 mg/kg twice daily.

Entry with first dose: within 1 hour pre-dose, and 1-2 hours, 6-10 hours, 20-24 hours post-dose.

After second dose: PK sample obtained 3-6 hours post-dose with laboratory evaluations.

Day 6-9 of life: within 1 hour pre-dose of initiating 3mg/kg twice daily. A physical exam will also be conducted at this visit.

Day 15-18 of life: within 1 hour pre-dose, and 1-2 hours post-dose, 4-6 hours post-dose, and 8-12 hours post-dose.

Day 28-32 of life: within 1-hour pre-dose of initiating 6 mg/kg twice daily.

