8.2 Outcome Measures

(Outcome Measures are for infants only; maternal data are to be used as covariates, not as outcomes)

8.21 Primary Endpoints for Cohorts 1 and 2

Toxicity Endpoints: Toxicity from study entry through 6 weeks of life

- Adverse events of Grade 3 or 4 severity or death (primary safety endpoint for final analysis)
- Suspected adverse drug reaction (SADR) of Grade 3 or 4 severity or death (primary safety endpoint for dose finding guidelines described in Section 8.52) but secondary safety endpoint for the analyses described in Section 8.71)

Pharmacokinetic Endpoints: (See Section 9.0: Clinical Pharmacology Plan)

8.22 Primary Response Variables for Cohorts 1 and 2 Pharmacokinetic parameters (See Section 9.0)

8.23 Secondary toxicity endpoints for Cohorts 1 and 2: Toxicity from study entry weeks through 24 weeks of age

- Adverse events of Grade 3 or 4 severity or death
- Suspected adverse drug reaction (SADR) of Grade 3 or 4 severity or death

8.24 Secondary Response Variables for Cohorts 1 and 2

- UGT1A1 genotype (presence or absence of *28/*28 genetic variant)
- SLCO1B3 (rs2117032-C/T) genotype
- Hyperbilirubinemia defined as total bilirubin exceeding 16.0 mg/dL or infant receiving phototherapy, or transfusion therapy, or other therapies for hyperbilirubinemia

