To assess the safety and tolerability of RAL through 24 weeks of life, descriptive statistics will be calculated summarizing the proportion of infants who had an adverse event of Grade 3 or 4 severity or death based on safety data from study entry through 24 weeks of age on all safety evaluable infants in each of the four study groups. A similar analysis will be done to summarize proportion of infants who had an SADR of Grade 3 or 4 severity or death.

To investigate the relationship between neonatal raltegravir elimination and UGT1A-1 genotype, participants will be divided into subgroups, based on whether or not they exhibit polymorphisms on UGT1A-1. Descriptive analyses will be performed to compare these subgroups with respect to measures of central tendency and dispersion for raltegravir AUC.

Similar descriptive analyses will also be performed to investigate the association of UGT1A1 (*28/*28) and SLCO1B3 (rs2117032-C/T) with hyperbilirubinemia. If the sample size and the data distributions make this possible, a logistic regression model predicting for probability of neonatal hyperbilirubinemia with UGT1A1 (*28/*28) genotype, SLCO1B3 (rs2117032-C/T) genotype, gestational age and gender as predictors will be fitted on the pooled data across the two cohorts. Note that the sample size may be too small and/or there may be insufficient cases of hyperbilirubinemia to make this possible. If this analysis can be done, it will have minimal power, but the size and directionality of effects will be compared with those predicted on the basis of previous findings.

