APPENDIX II-B - FOOTNOTES FOR INFANT SCHEDULE OF EVALUATIONS
FOR COHORT 2

1. History includes all non-protocol laboratory tests, HIV test results, antiretroviral agents (for PMTCT), concomitant medications, and any intercurrent illnesses since last visit.
2. Physical examination includes infant Apgar score, birth weight and length, gestational age, gender, and ethnicity.
3. Complete physical examination includes temperature, blood pressure, heart rate, respiratory rate, weight, length, and head circumference.
4. Pre and post-dose monitoring includes a telephone call by study staff to review medication instructions and check any side effects. Clinic staff will call the participant's home prior to PK sampling days to confirm adherence, understanding of dosing, and no intercurrent illnesses that might preclude PK sampling. If correct doing for 48 hours prior to PK sampling is not confirmed, PK sampling will be rescheduled. Post PK sampling visit days, study staff will review for adverse events and answer any questions for participants' parents by phone. If adverse events are noted, early return visits to clinic may be arranged.
5. Hematology includes CBC (complete blood count) with differential and platelet count which may be obtained any time on the first day of life.
6. Chemistries include AST, ALT, creatinine, and total and direct bilirubin which must be obtained prior to enrollment of the infant.
7. Only total and direct bilirubin required.
8. HIV NAT may be either HIV RNA or HIV DNA. Collect 1-3mL depending on the type of platform performed at the site.
9. Obtain HIV NAT at entry if NOT done as part of standard of care.
10. Participants with confirmed vertical transmission should have 2mL of blood drawn for viral resistance testing to raltegravir and other ARVs as soon as possible after confirmation of HIV infection and should have safety assessments as described in Appendix II-C.
11. Genotyping (optional) for UGT1A1 and SLCO1B1 polymorphisms will be done using dried blood spot on filter paper which may be obtained with any blood sample.
12. Collect PK samples at time points as specified in Section 3.0.
13. Acceptable methods of blood collection for PK samples and laboratory evaluations are by venipuncture, heel stick or indwelling line.
14. When possible, an assessment of infant feeding (type and time of last infant feeding prior to RAL dose) should be recorded.

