4.9 Genotype Analysis

Purpose:

To list the tables for investigating the relationship between neonatal RAL elimination (as reflected in CL/F) and UGT1A-1 genotype, and the relationship between UGT1A-1 and SLCO1B3 with hyperbilirubinemia.

Analysis Program Validation:

Code review required.

Data:

HUMGENO table and LBW0093 CRF (TBILCV, BILPHOTO, BILTRANS, BILOTH and BILOTHSP).

Analysis:

- a) Response variables for genotype analysis:
 - UGT1A-1 genotype (presence or absence of *28/*28 genetic variant):
Wild-type: (TA)₆(TA)₆; mutation: (TA)₅(TA)₆, (TA)₆(TA)₇ and (TA)₇(TA)₇
 - SLCO1B3 (rs2117032-C/T) genotype:
C/C, C/T and T/T
 - Hyperbilirubinemia defined as total bilirubin exceeding 16.0 mg/dL or infant requiring exchange transfusion for hyperbilirubinemia

b) Output tables:

Table: Summary descriptive statistics (N, geometric mean, median, 25th and 75th percentiles, min, and max) on CL/F will be generated for the subgroups of participants depending on whether they exhibit the UGT1A1 polymorphism.

Table 8: Summary of Infant RAL CL/F between UGT1A1 Genotype Groups for Cohort 1 (mock-up table)

		UGT1A1 Genotypes					Overall	p-value ^a for all genotypes	p-value ^b for wild-type vs. mutation
		Wild-type	Mutation			Overall			
		(TA)6(TA)6	(TA)5(TA)6	(TA)6(TA)7	(TA)7(TA)7				
CL/F of RAL-naïve Infants	N								
	mean								
	median								
	...								
CL/F of RAL-Exposed Infants	N								
	mean								
	median								
	...								
CL/F of All Infants	N								
	mean								
	median								
	...								

a Comparison of median among different genotypes will use Kruskal–Wallis test for CL/F of all infants only. The formal comparison will be done only if we have enough infants in the listed genotype groups.

b Comparison of median between wild-type vs. mutation will use Wilcoxon Rank Sum Test for CL/F of all infants only. The formal comparison will be done only if we have enough infants in the listed genotype groups.

**Table 9: Summary of Infant RAL CL/F between UGT1A1 Genotype Groups for Cohort 2
(mock-up table)**

		UGT1A1 Genotypes					Overall
		Wild-type	Mutation			Overall	
		(TA)6(TA)6	(TA)5(TA)6	(TA)6(TA)7	(TA)7(TA)7		
CL/F from the 1st intensive PK analysis	N						
	mean						
	median						
	...						
CL/F from the 2nd intensive PK analysis	N						
	mean						
	median						
	...						

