Note: This table is for Cohort 2 RAL-naïve group only and should we have data on Cohort 2 RAL-exposed group, additional columns for: (i) RAL-exposed group, and (ii) Overall Cohort 2, will be added. Formal comparisons for all Cohort 2 infants will be done by then.

Table: Association between UGT1A-1 genotypes and hyperbilirubinemia (yes/no) with Fisher’s Exact Test.

Table 10: Summary of Cohort 1 Infant Hyperbilirubinemia between UGT1A1 Genotype Groups (mock-up table)

Characteristic		Wild-type	Mutation				Overall (N=0)	P-value* for all genotype groups	P-value* for Wild-type vs. Mutation
		(TA)6(TA)6	(TA)5(TA)6	(TA)6(TA)7	(TA)7(TA)7	Overall			
Hyperbilirubinemia	Yes	0	0	0	0	0	0.000	0.000	
	No	0	0	0	0	0			

*Fisher’s Exact Test. The power of test will depend upon the distributions of the variables to be analyzed, but will be extremely limited due to the small sample size.
Note: Similar table will be created for Cohort 2 infants.

Table: Association between SLCO1B3 genotypes and hyperbilirubinemia (yes/no) with Fisher’s Exact Test.

Table 11: Summary of Cohort 1 Infant Hyperbilirubinemia among SLCO1B3 Genotype Groups (mock-up table)

Characteristic		C/C (N=0)	C/T (N=0)	T/T (N=0)	Total (N=0)	P-Value*
Hyperbilirubinemia	Yes	0	0	0	0	0.000
	No	0	0	0	0	

*Fisher’s Exact Test. The power of test will depend upon the distributions of the variables to be analyzed, but will be extremely limited due to the small sample size.
Note: Similar table will be created for Cohort 2 infants.

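### SAP 4.9 tests the genotypes only against yes/no hyperbilirubinemia, although bilirubin levels are collected repeatedly; a supportive rank and trend analysis of the level would recover information at little cost

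*SAP*

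**What the plan says.** - **Tests.** SAP 4.9 lists "Association between UGT1A-1 genotypes and hyperbilirubinemia (yes/no) with" Fisher's exact test (Table 10) and "Association between SLCO1B3 genotypes and hyperbilirubinemia (yes/no) with" Fisher's exact test (Table 11). The mock-ups are for Cohort 1, with similar tables for Cohort 2. C/C, C/T and T/T are treated as unordered. Footnotes say power will be extremely limited because the sample is small.
- **Outcome.** SAP 4.9 uses "Hyperbilirubinemia defined as total bilirubin exceeding 16.0 mg/dL or infant requiring exchange transfusion for hyperbilirubinemia". Protocol 8.24 is wider: "Hyperbilirubinemia defined as total bilirubin exceeding 16.0 mg/dL or infant receiving phototherapy, or transfusion therapy, or other therapies for hyperbilirubinemia".
- **Data.** In Cohort 2, Protocol 3.0 has "chemistry laboratory evaluations performed at all study visits", and Appendix II-B explains: "Chemistries include AST, ALT, creatinine, and total and direct bilirubin which must be obtained prior to enrollment of the infant". A bilirubin-only repeat follows the second dose. Appendix II-A schedules bilirubin in Cohort 1 at entry, Day 3-4, before Dose 2, and at 2, 6 and 24 weeks. SAP 4.9 already lists TBILCV among its inputs, read here as the total bilirubin value.
- **Rank tests nearby.** For CL/F, the same SAP section uses Wilcoxon and Kruskal-Wallis tests.
- **Protocol 8.711.** It plans descriptive analyses of genotype and hyperbilirubinemia and, if the data allow, a logistic regression pooled over cohorts. For that regression, "the size and directionality of effects will be compared with those predicted on the basis of previous findings". SAP 4.9 does not carry the regression over.

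**The concern.** A measured quantity is cut at a high threshold and only the resulting yes/no is tested. Infants at 6 and at 15 mg/dL count the same. With few infants above 16.0 mg/dL, the tables rest on a handful of events. The SAP definition makes events rarer still: an infant given phototherapy below the cut is a non-event in Tables 10 and 11, though an event under Protocol 8.24. The unordered test for SLCO1B3 also ignores the order in number of alleles.

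The SAP attributes the low power to sample size alone. Dichotomising is a second cause, and one that can be avoided. At stake is how much the bilirubin half of secondary objective 2.22 can say. No dosing or safety decision depends on these tests.

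**Working it through.** The documents give no power, significance level, event rate, genotype frequency or bilirubin SD for these tests, so there is no stated figure to reproduce. A two-sided 5% level is assumed throughout.

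**1. Sample sizes (documents).** Cohort 1: 10 + 6 = 16. Cohort 2: 26 RAL-naïve (SAP 2) + at least 8 RAL-exposed (Protocol 8.4) = 34. All: 16 + 34 = 50. Genotyping is optional, so the analysed numbers may be smaller.

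**2. Events Fisher needs if the two genotype groups are equal.** With E events all in one group, the two-sided p is 2·C(n/2, E)/C(n, E).
- n=16, E=4: 2·70/1820 = 0.077. n=34, E=4: 2·2380/46376 = 0.103.
- At n=26 and n=42, four events give 0.096 and 0.107. Five events give 0.026, 0.039, 0.045 and 0.048 at n=16, 26, 34 and 42.

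So with equal groups, four events or fewer can never reach p<0.05. This does not carry over to a small carrier group: with 5 carriers of 34, two events both in carriers give C(5,2)/C(34,2) = 10/561 = 0.018.

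**3. Expected events, unequal groups.** Assumed: normal peak bilirubin, mean 9, SD 4 mg/dL, cut 16, 15% carriers.
- Non-carriers: 1 − Φ((16 − 9)/4) = 1 − Φ(1.75) = 0.040.
- Carriers 4 mg/dL higher: 1 − Φ(0.75) = 0.227. Carriers 2 mg/dL higher: 1 − Φ(1.25) = 0.106.
- n=34, 4 mg/dL: 28.9 × 0.040 + 5.1 × 0.227 = 2.3 events. n=16: 13.6 × 0.040 + 2.4 × 0.227 = 1.1 events.

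**4. Simulated power, same assumptions.**

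| n | Shift (mg/dL) | Fisher | Rank test on level |
|---|---|---|---|
| 34 | 4 | 18% | 47% |
| 34 | 2 | 5% | 16% |
| 16 | 4 | 5% | 17% |
| 16 | 2 | 1% | 6% |

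With treated infants tied at the top, the 47% falls to about 42%. For all 50 infants and a 4 mg/dL shift, the figures are about 31% and 63%.

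**5. Dependence on the event rate.** Two equal groups, n=34, shift of 1 SD:

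| Event rate | Fisher | Wilcoxon | Share of power lost |
|---|---|---|---|
| 5% | 0.01 | 0.79 | 99% |
| 10% | 0.11 | 0.78 | 86% |
| 20% | 0.32 | 0.77 | 58% |
| 40% | 0.47 | 0.79 | 41% |

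The last column is 1 − Fisher/Wilcoxon.

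**6. Three genotypes.** n=34, allele frequency 0.5, shift of 0.5 SD per allele (2 mg/dL if SD is 4). At event rates of 5%, 10% and 20%, the 2×3 Fisher test has power 0.05, 0.10 and 0.18. Kruskal-Wallis has about 0.36 and a linear trend test about 0.50. On the mg/dL scale with the cut at 16, 2 mg/dL per allele gives about 12% for Fisher and 47% for a trend test.

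**The case against.** The case for leaving the plan alone is substantial.

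- **The binary outcome is the stated question.** Objective 2.22 and Protocol 8.24 both name hyperbilirubinemia, and the Fisher tables test it. This stands, and is why they should stay.
- **Low power is disclosed** in Protocol 8.711 and in the SAP footnotes. This stands too, though neither mentions dichotomising as a cause.
- **The level is harder to analyse than it looks.** Phototherapy follows local practice and lowers later values, sampling ages vary, and a peak from a few samples is noisy. This stands as a limit on the gain. The top-tie rule costs some power in simulation but leaves most of the advantage.
- **Power stays low after the change**, at 17% or less for n=16 in step 4. This stands for Cohort 1.

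A reader might also infer more than the documents support:

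- *That the Fisher tests are the only planned association analyses.* Protocol 8.711 also plans descriptive analyses and the conditional logistic regression. That regression is binary as well, so it does not use the level either.
- *That the Fisher tables are to be set against previous findings.* That comparison belongs to the regression.
- *That a yes/no result is on the wrong scale for the earlier evidence.* For SLCO1B3 this rests on one background sentence in Protocol 1.27, that the variant "was found to have a strong association with bilirubin levels in neonates". The title of the association study cited there refers to neonatal hyperbilirubinemia.

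**Conclusion.** The point holds as a low-priority improvement to a secondary analysis. SAP 4.9 plans no genotype analysis of bilirubin level, although the values are scheduled repeatedly and are already among its inputs. For the Cohort 2 tables, a rank test would have roughly two and a half to three times the power of Fisher under the assumed distribution (47/18 = 2.6; 16/5 = 3.2).

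The mean, SD, shift and carrier share are all assumed, so these figures are illustrative. A flat statement that most of the power is discarded would go too far: in step 5 the loss runs from about 41% at a 40% event rate to nearly all of it at 5%. Nor would the change make Cohort 1 informative. It would give the secondary objective an estimate in mg/dL and a better chance in Cohort 2 or in the pooled data.

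**What to change.** Keep the Fisher tables for the stated outcome, and add to SAP 4.9 an analysis labelled exploratory and supportive:

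- **Variable:** peak total bilirubin after the first dose through the Day 6-9 visit (the Dose 2 visit in Cohort 1). The entry sample is excluded because it precedes dosing.
- **Ranking rule:** infants with more than 16.0 mg/dL, or given phototherapy or exchange transfusion, are tied at the top. A sensitivity analysis uses observed values.
- **Tests:** exact Wilcoxon for UGT1A1 wild-type versus mutation; exact trend test (Jonckheere) across C/C, C/T, T/T; stratified by cohort when pooled.
- **Estimate:** median difference with a confidence interval. Take it from the observed values, since the top tie has no value in mg/dL.
- **Reporting:** the number genotyped and the number tied at the top, by cohort.

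The cost is one derived variable and two tables, with no new data and no change to patient management. The downside is noise from local phototherapy practice and varying sample ages, which the text should state.
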